#### 4.2 Unblinding and Crossover Subjects

All subjects will be un-blinded after the assessment is complete at the 3-month time point. If the subject is in the Sham Control group, a Latera implant may be implanted if they meet the eligibility criteria. Subjects who are un-blinded (within either treatment arm) prior to the 3-month time point will be excluded from the per protocol analysis dataset for primary and secondary analysis endpoints. However, data will continue to be recorded through the 24-month follow-up time point for these subjects.

<sup>2 Fisher LD, Dixon DO, Herson J, Frankowski RK, Hearon MS, Pearce KE. Intention to treat in clincial trials. In: Pearce KE, ed. Statistical issues in drug research and development. New York: Marcel Dekker; 1990:331-50

### STATISTICAL ANALYSIS PLAN

Sham Control subjects may not receive a nasal implant prior to the 3-month primary endpoint assessment.

Cross-over subjects will have 2 additional visits as they will begin follow-up time points again once they have received the Latera Implant.

#### 5 STATISTICAL ANALYSES

#### 5.1 General Considerations

All statistical programming will be performed using SAS® version 9.4 or above.

Descriptive summary statistics will be presented for all data points. When data are not available, or partially available data summaries will be based on available data. For continuous variables, number of observations, mean, standard deviation (SD), median, minimum, maximum and, for some variables, the 95% confidence interval (CI) will be presented. For categorical variables, numerator, denominator, percentage (%) and for some variables, the 95% CI will be presented. In both cases the difference between treatment and control as well as 95% CI of the difference may be presented. When presented, the 95% CI will be calculated using the exact method.

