This Clinical Investigational Plan (CIP), informed consent forms (ICF), recruitment materials, and all participant materials will be submitted to the Institutional Review Board (IRB) for review and approval. Approval of the CIP and the ICF must be obtained before any subject is enrolled. Any amendment to the CIP will require review and approval by the IRB before the changes are implemented to the study. In addition, all changes to the ICF will be IRB-approved and a determination will be made regarding whether a new consent needs to be obtained from subjects who previously provided consent.

INVESTIGATOR SIGNATURE PAGE

Investigator Name

Title

Site Name

Site Number

Date

I have read the protocol and agree that it contains all necessary details for carrying out this study. I will conduct the study as outlined therein.

I agree to keep records on all subject information (e.g., source documents and informed consent forms), device shipments and return forms, and all other information collected during the study, in accordance with local and national regulations.

Investigator Signature

SYNOPSIS

Study Title	Latera RCT – Latera [®] Absorbable Nasal Implant vs. Sham Control for Lateral Nasal Valve Collapse		
Spirox Protocol Number	CP04		
Investigational Device	Spirox Latera Absorbable Nasal Implant		
ClinicalTrials.gov Identifier	NCT 03400787		
Sponsor	Spirox, Inc. [name]		
Study Purpose	To evaluate the Latera Absorbable Nasal Implant (Latera Implant) Implant versus Sham Control in subjects with nasal valve collapse due to or primarily due to insufficient cartilaginous support of the lateral nasal wall		
Objective	The primary objective of the LATERA RCT is to demonstrate the superiority of the Latera Implant to improve nasal breathing, compared with a Sham Control treatment.		
Phase of Study	Post-market		
Study Design	Randomized (1:1), sham-controlled, single-blind, multicenter pos market trial using an adaptive trial design		
Investigational Sites	Up to 15 investigational sites in the United States, in office-based locations with investigators experienced in standard nasal interventions for airway obstructions and the use of the Latera Implant		
Study Population	The Adaptive Design allows for enrollment of up to 150 subjects with nasal airway obstruction due to or primarily due to nasal valve collapse.		

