#### 2.4 Sample Size Considerations

The primary analysis will be based on a 1-sided binomial test of proportions. Assuming a Sham Control response rate of 40% and a Latera Treatment response rate of 70% at month 3, a maximum sample size of 124 evaluable subjects is required for 90% power and preserving a 2.5% (one-sided) type I error rate. This study is designed as a group-sequential trial with 2 interim analyses and a final analysis. The stopping boundaries are derived using the Triangular

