# STATISTICAL ANALYSIS PLAN

Method, which is a special case of Unified Family (Power) boundaries. A shape parameter of 0.65 will be used, and both boundaries will be non-binding.

Interim analyses will occur when approximately 20 and 60 total subjects have been enrolled and have had their 3-month assessment. The Latera response rate has been observed at approximately 85% in single-arm trials and is likely to be slightly lower in a single blind setting. Thus, 70% is likely a conservative estimate. The placebo response rate observed in pain trials is approximately 30%, and may be even higher in a procedural setting, so 40% was selected for the control response rate used in the study design calculations.

Assuming up to a 10% drop out rate and a 10% potential retrieval rate, the sample size is adjusted to enroll up to 150 subjects to assure adequate sample size with 3 months follow up.

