## STATISTICAL ANALYSIS PLAN

The treatment  $(p_T)$  and control  $(p_C)$  will be compared using a 1-sided test for superiority of the following hypothesis:

H0:  $p_T \le p_C$  versus HA:  $p_T > p_C$ 

Where p is the proportion of subjects with a positive response on the primary endpoint assessment. Successful rejection of the null hypothesis will be taken as evidence the device provides reasonable assurance of effectiveness.

A 1-sided binomial test of proportions will be used to compare treatment groups.

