#### 5.4.4 Interim Analyses

There will be two planned interim analyses and one final analysis for this study (**Table 1**, below). The stopping boundaries are derived using the Triangular Method [see footnote 1], which is a special case of Unified Family (Power) boundaries. A shape parameter ( $\tau$ ) of 0.65 will be used, and both boundaries will be non-binding. Interim analyses will occur when approximately 22 and 60 total subjects have been enrolled with 3-month assessments. The stopping boundaries are

ST 800-A

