### STATISTICAL ANALYSIS PLAN

moderately aggressive for both effectiveness and futility to reduce the number of subjects enrolled if clear evidence of effectiveness or futility becomes apparent during the trial. When the design assumptions are correct (40% versus 70%), the chance that the trial will stop for effectiveness at the second interim analysis is about 1 in 3. However, if the Latera rate is 85% as seen in the single arm studies, the chance of stopping for effectiveness at the second interim analysis is better than 8 in 10. While all evaluable subjects enrolled at the time of the interim analysis would be followed through 3 months and included in the primary endpoint, an early termination at the second interim analysis could save 20-30% of the total sample size, depending on the enrollment rate.

Interim analyses will be carried out by an independent statistician and reviewed by the independent DMC. The interim analyses will use an alternative to the critical ratio test given below and described by Fleiss. The test results will be compared to the triangular group sequential boundaries. Additional operational details will be found in the DMC Charter.

$$z' = \frac{|p_2 - p_1| - \frac{1}{2}(1/n_{1.} + 1/n_{2.})}{\sqrt{\frac{p_1 q_1}{n_{1.}} + \frac{p_2 q_2}{n_{2.}}}}.$$

			ndaries value)	Cumulative Error Spending		
Analysis	Evaluable (n)	Futility	Efficacy	Type II	Type I	
Interim 1	22	0.7921	0.0005	0.0106	0.0005	
Interim 2	60	0.2139	0.0090	0.0548	0.0093	
Final	124	0.0194	0.0194	0.1000	0.0250	

Table 1. Group Sequential Trial Design – Boundary Information

<sup>3 Fleiss JL, B Levin, MC Paik. Statistical Methods for Rates and Proportions, 3rd Ed. John Wiley & Sons, 2003, (Ch. 3, p 61).

ST 800-A

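### The 95% CI rule does not match the group-sequential decision rule, and no adjusted estimate is planned for the primary responder difference after an early stop

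*SAP*

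**What the plan says.** SAP 5.1 (General Considerations) allows the treatment difference and its 95% CI to be shown for any variable and adds: "When presented, the 95% CI will be calculated using the exact method". It names no exact variant and does not mention the sequential design.

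SAP 5.2 gives the primary analysis in one sentence: "A 1-sided binomial test of proportions will be used to compare treatment groups". It does not say whether the variance is pooled or whether a continuity correction applies.

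SAP 2.4 plans "a maximum sample size of 124 evaluable subjects is required for 90% power and preserving a 2.5% (one-sided) type I error rate". SAP 5.4.4 times the looks: "Interim analyses will occur when approximately 22 and 60 total subjects have been enrolled with 3-month assessments". Its boundary table, repeated in Protocol 6.8, sets one-sided efficacy p-values of 0.0005, 0.0090 and 0.0194 at 22, 60 and 124 evaluable subjects. The interim statistic is an unpooled, continuity-corrected z'.

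On an early stop, SAP 5.4.4 says that "all evaluable subjects enrolled at the time of the interim analysis would be followed through 3 months and included in the primary endpoint". The table has no row for that enlarged analysis. Neither document gives an adjusted estimate, a sequential CI, or a CI level tied to the bounds.

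**The concern.** Readers of a trial report take the point estimate and CI as the size of the benefit, and expect the CI to agree with the test. Here the two use different error rates. At the final look the test needs p at or below 0.0194, while a 95% CI excludes zero once the one-sided p is at or below 0.025.

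A trial stopped because its interim difference was large also tends to report a difference that is too large. The plan offers no second estimate to show this. Overrun adds a further gap: the primary analysis after a stop is run at an information level with no stated bound, and nothing says whether the claim rests on the boundary crossing or on the later p-value. A choice made after an unblinded look would be data-driven.

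**Working it through.** **Inputs.** Rates from SAP 2.4: "Assuming a Sham Control response rate of 40% and a Latera Treatment response rate of 70% at month 3". Allocation from the Protocol synopsis: "Randomized (1:1), sham-controlled, single-blind", hence 11, 30 and 62 per arm at the three looks. Bounds from the SAP 5.4.4 table. Interim statistic z' from SAP 5.4.4. Assumed: equal arms at each look, futility bounds followed unless stated, and overrun subjects responding at the true rates.

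**1. The plan's own figures.** Three-look normal process with information fractions 22/124 = 0.177, 60/124 = 0.484 and 1, and variance 0.4×0.6 + 0.7×0.3 = 0.45. The tabled bounds give cumulative type I error 0.0005 / 0.0093 / 0.0251 (futility ignored), type II error 0.0108 / 0.0546 / 0.0987, and power 90.1%. The table reproduces within rounding.

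**2. CI level.** The level that matches the final bound is 1 − 2×0.0194 = 0.9612, not 0.95.

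**3. Normal approximation.** SE = √(0.45/62) = 0.0852 at the final look and √(0.45/30) = 0.1225 at interim 2. The stage-wise ordering ignores the futility bound, as a non-binding design requires.

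| Result | Naive estimate (95% CI) | Stage-wise 95% CI |
|---|---|---|
| Final, z = 2.066 (on the bound) | 0.176 (0.009 to 0.343) | 0.000 to 0.341 |
| Final, z = 2.00, p = 0.0228 (fails) | 0.170 (0.003 to 0.337) | −0.005 to 0.335 |
| Interim 2, z = 2.366 (on the bound) | 0.290 (0.050 to 0.530) | 0.049 to 0.529 |

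At the final look the stage-wise interval restores agreement with the test. At interim 2 it changes almost nothing; the median-unbiased estimate is 0.289 against 0.290. If the ordering treats futility as binding, the z = 2.00 interval becomes 0.0001 to 0.364 and the conflict survives.

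**4. Individual tables with exact CIs.** An exact CI excludes zero when the exact one-sided p at zero difference is at most 0.025.
- Sham 25/62, Latera 37/62. Corrected z = (12/62 − 1/62)/0.0881 = 2.014, p = 0.0220, so the trial fails. The exact p is 0.0192, so the CI excludes zero. An uncorrected test gives p = 0.0140 and there is no conflict.
- Sham 20/62, Latera 31/62. The uncorrected p is 0.0206 (unpooled) or 0.0223 (pooled), so the trial fails. The score-ordered exact p is 0.0241 (CI excludes zero); the exact p ordered by risk difference is 0.0294 (CI includes zero).
- At 62 v 62 the risk-difference-ordered p steps from 0.0192 (12 more responders) to 0.0294 (11 more). No table then conflicts with an uncorrected test. At 61 v 63 such tables appear, for example 21/61 v 33/63.

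**5. How often.** Exact binomial enumeration at 11/30/62 per arm with z' at the interims; probability that the trial fails at the final look while the exact CI excludes zero:

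| Final test | Exact variant | 40 v 70 | 40 v 60 | 40 v 55 |
|---|---|---|---|---|
| Continuity-corrected | risk difference | 1.9% | 4.3% | 3.8% |
| Continuity-corrected | score | 2.5% | 5.0% | 4.7% |
| Uncorrected | risk difference | 0 | 0 | 0 |
| Uncorrected | score | 0.5-0.7% | 0.6% | 0.8-0.9% |

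**6. Average overstatement at a true 0.30** (same enumeration).
- Interim 1 efficacy stop (probability 0.07): mean observed difference 0.676.
- Interim 2 efficacy stop (probability 0.39): mean 0.399, or 0.378 if the interim test is uncorrected.
- All stops together: 0.329, a bias of about +0.03.
- Overrun after interim 2. A saving of 20-30% leaves 87-99 of 124, or 105-120 of 150. With 87 analysed, (60×0.399 + 27×0.30)/87 = 0.368. The other sizes give 0.360 (99), 0.357 (105) and 0.350 (120).
- At 40% v 85%, the interim 2 mean is 0.451 against 0.45. Only interim 1 stops overstate (0.691).

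**7. Bias-adjusted mean.** This is the difference whose expected naive estimate equals the one observed. Under the normal model 0.333 becomes about 0.307 and 0.40 becomes about 0.366.

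**The case against.** The CI rule stands among descriptive summaries, and the CI of the difference is optional. Success is judged by the p-value against its bound and never by the CI. That stands. A reader might infer that the trial's false-positive rate is inflated; the documents do not support this, because the tabled bounds hold type I error at 0.025 whatever interval is printed.

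A reader might also infer that any early stop overstates the benefit. The figures are averages over stops, they shrink once the planned overrun is included, and at 40% v 85%, where the SAP rates an interim 2 stop most likely, the interim 2 excess is negligible. Nor is the CI-test conflict certain: with equal arms, an uncorrected final test and risk-difference ordering it does not occur. Its frequency depends on choices that the SAP leaves open.

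A stage-wise interval with its median-unbiased estimate might look like a full remedy. It repairs the final look but leaves an interim 2 result almost unchanged, so the early-stop bias needs a different estimate.

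The DMC Charter, which was not supplied, may cover overrun operations. The estimate and interval for the primary endpoint still belong in the SAP.

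**Conclusion.** The concern holds as a reporting fault of moderate size. Followed as written, SAP 5.1 gives an interval that is inconsistent with the decision rule. At the final look it can exclude zero in a failed trial: about 0-2.5% of trials at 40% v 70% and 0-5% at 40% v 55-60% for exact CIs. After an early efficacy stop the naive difference is too high on average. The excess is large at interim 1, about 10 points at interim 2 before overrun and 5-7 after it, and about 3 points over all stops. The planned overrun analysis has no stated bound or role.

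These sizes rest on equal arms at each look, futility bounds being followed, and overrun subjects responding at the true rates. The ranges reflect the unnamed final test and exact variant.

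**What to change.** In SAP 5.1 and 5.2, before any unblinded look:
- Name the final test (variance form, continuity correction) and build the primary CI from the same test form.
- Pre-specify a sequentially adjusted 95% CI for the primary difference: stage-wise ordering through PROC SEQTEST, which fits the PROC SEQDESIGN code already in the SAP, with the non-binding futility bound ignored in the ordering. The minimum alternative is a 96.1% CI at the final look.
- After an early stop, report a bias-adjusted mean beside the naive estimate. Label the naive estimate and CI descriptive.
- State that after an efficacy stop the claim rests on the boundary crossing, and that overrun subjects enter the adjusted estimate at their actual information level.

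The cost is SAP wording, a few lines of SAS, a little more analysis work, and a slightly less favourable reported effect. Sample size, bounds and trial conduct do not change.

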#### 5.2 Primary Endpoint Analysis

The primary endpoint of the study is defined as the proportion of responders at 3 months following the index procedure. Responder is defined as a subject that has at least one (1) NOSE class improvement or at least 20% NOSE score reduction from baseline to 3 months post treatment.

## STATISTICAL ANALYSIS PLAN

The treatment  $(p_T)$  and control  $(p_C)$  will be compared using a 1-sided test for superiority of the following hypothesis:

H0:  $p_T \le p_C$  versus HA:  $p_T > p_C$ 

Where p is the proportion of subjects with a positive response on the primary endpoint assessment. Successful rejection of the null hypothesis will be taken as evidence the device provides reasonable assurance of effectiveness.

A 1-sided binomial test of proportions will be used to compare treatment groups.

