Effectiveness of the device was assessed using the NOSE scores through follow-up time points at 1 month, 3 months, 6 months, 12 months, 18 months, and 24 months. The NOSE score is a validated scoring system for nasal obstruction.¹⁷ The NOSE scores are assessed using a validated questionnaire using patient responses to a set of five (5) questions. A percent responder rate was calculated at each follow up time point to assess the proportion of subjects that noted a benefit. Responder Rate is defined as the proportion of subjects with at least one (1) NOSE class improvement or at least 20% NOSE score reduction. The NOSE Categories are as follows: mild 5-25 points, moderate 55-75 points, extreme 80-100 points. The responder rate was 86.7% at 1 month, 86.2% at 3 months, and continued improvement of 80% at 24 months. External and internal physical examination findings were normal, without evidence of implant migration. Results from an independent physician review of collected photographs demonstrated an adverse cosmetic effect at the 3-month follow-up time point in 1/30 subjects (3%). **Figure 1** (page 16, below) summarizes the study results. The 12-month results were reported in the medical literature in April 2017. The 24-month follow up was completed in July 2017.

In summary, the results of the first 30-subject clinical trial demonstrated safety and effectiveness of the device for the support of upper and lower lateral cartilage. The per subject ADE rate was comparable to the rates reported in published studies of other alloplastic materials used to provide lateral cartilage support in similar study populations.

^a The INEX device was used in this study, a predecessor device of Latera. Latera is substantially equivalent to INEX, with modifications to device packaging and changes to enhance usability.

Figure 1. 24-Month Results from Spirox First Study; Percent Responders (NOSE Score)

Additional Studies

Spirox is currently sponsoring two additional studies on the Latera Implant, LATERAL OR and LATERAL Office studies (NCT#02952313 and NCT#02964312, respectively). While enrollment was very recently completed, some unmonitored, unpublished study results are available. Please note: these data are provided to share Latera experience in a broader patient population and based in the U.S. Current data is preliminary and is subject to change.

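### The primary responder test is valid but ignores baseline NOSE, on which the responder rule depends; adjusting for it at the final analysis would bring a modest gain in precision

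*SAP*

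**What the plan says.** The responder rule in SAP 5.2, applied at the 3-month visit, is: "Responder is defined as a subject that has at least one (1) NOSE class improvement or at least 20% NOSE score reduction from baseline". The classes appear only in Protocol 1.2, in the account of the first study: "The NOSE Categories are as follows: mild 5-25 points, moderate 55-75 points, extreme 80-100 points". Scores of 30-50 fall in no listed class, and the SAP defines no classes at all.

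The test is stated in SAP 5.2: "A 1-sided binomial test of proportions will be used to compare treatment groups". The interim statistic in SAP 5.4.4 is also unadjusted; it is a continuity-corrected difference over an unpooled standard error. No stratified, adjusted or standardised analysis of the primary endpoint is planned, even as a sensitivity analysis. Protocol 5.2 describes assignment lists by site and mentions no stratification by NOSE.

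Baseline NOSE is the first item collected at screening (Protocol 5.1), entry requires a score of at least 55 (Protocol 4.1), and SAP 5.5 uses the score as a predictor in the imputation model.

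SAP 2.4 sizes the trial on assumed responder rates of 40% for sham and 70% for Latera, with this result: "a maximum sample size of 124 evaluable subjects is required for 90% power and preserving a 2.5% (one-sided) type I error rate".

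**The concern.** A subject's chance of being a responder depends partly on where the subject starts, because the rule asks for a different drop at different baselines. That holds even if improvement in points is unrelated to baseline. The plan relies on baseline NOSE to predict the outcome when the outcome is missing, but leaves it out of the one confirmatory comparison. Two things are at stake: some avoidable variance in the estimated difference, and some exposure of that estimate to chance imbalance in baseline NOSE between the arms.

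**Working it through.** **1. The plan's own figure.** Inputs: 40% v 70%, one-sided 0.025, 90% power, 1:1 allocation (Protocol synopsis), looks at 22, 60 and 124 evaluable, triangular boundaries with shape 0.65 (SAP 2.4 and 5.4.4).

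- Fixed-sample total, unpooled variance: 2 x (1.960 + 1.282)^2 x (0.24 + 0.21) / 0.30^2 = 105.1.
- The boundary at these looks gives efficacy p-values of 0.0005, 0.0090 and 0.0194, as printed. The inflation factor is 1.172.
- 105.1 x 1.172 = 123.2, which is 124 with equal arms. The printed boundaries at 124 give cumulative one-sided error 0.0251 and power 0.901 with futility stopping followed.

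So 124 reproduces without any adjustment.

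**2. How the rule depends on baseline.** Five items scored 0-4 on a 100-point scale imply 5-point steps (inferred). The smallest responding drop is the lesser of 20% of baseline, rounded up to a step, and the drop that leaves the class.

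| Baseline | 20% route | Class route | Smallest drop |
|---|---|---|---|
| 55 | 15 | 5* | 5* |
| 60 | 15 | 10* | 10* |
| 65 | 15 | 15* | 15 |
| 70 | 15 | 20* | 15 |
| 75 | 15 | 25* | 15 |
| 80 | 20 | 5 | 5 |
| 85 | 20 | 10 | 10 |
| 90 | 20 | 15 | 15 |
| 95 | 20 | 20 | 20 |
| 100 | 20 | 25 | 20 |

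*Only if 30-50 counts as a class. If it does not, 55 and 60 need 15.

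As a share of baseline this runs from 5/80 = 6% to 15/65 = 23%. There are four distinct values over ten scores, in a saw-tooth.

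**3. What adjustment is worth.** Write m1 and m0 for the response probabilities given baseline in each arm, averaging 0.70 and 0.40. The variance factor is V0 = 2(0.24 + 0.21) = 0.90 unadjusted, and V = 2E[m1(1 - m1)] + 2E[m0(1 - m0)] + Var(m1 - m0) adjusted. The equivalent sample size is 124 x V/V0.

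| Variance removed | Equivalent N | Power at 124 |
|---|---|---|
| 0 | 124 | 90.1% |
| 2% | 121.5 | 90.7% |
| 5% | 117.8 | 91.5% |
| 10% | 111.6 | 92.8% |
| 15% | 105.4 | 94.0% |

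The documents give no baseline distribution, spread of change or slope, so these were assumed: four baseline distributions on 55-100 (uniform, and normal with mean/SD 75/12, 70/10 and 80/12), SD of change 15-30 points, slope of change on baseline -0.3 to 0.6, and 30-50 treated as a class.

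- NOSE as categories removes 1-15% of the variance, median 3.5% (0.035 x 124 = about 4 subjects).
- If change is unrelated to baseline, so that only the rule acts, it removes 1-6%.
- A linear NOSE term alone removes 0-12%, median 1.3%, because it cannot follow the saw-tooth.
- Score plus class, in a separate set of nine scenarios (baseline mean 76, SD 13; residual SD 15-25; slope of follow-up on baseline 0.5-1; class route only from 80-100), explained 1.4-12% of within-arm variance.

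**4. Chance imbalance.** At 62 per arm the standard error of the difference is sqrt(0.45/62) = 0.085. With 1.4-12% of variance explained, the correlation is 0.12-0.35. A one-standard-error imbalance in baseline then moves the estimate by 0.085 x 0.12 to 0.085 x 0.35, or about 1-3 percentage points.

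**5. Type I error of the candidate fixes**, simulated against the printed boundaries:

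| Procedure | One-sided error |
|---|---|
| Unadjusted unpooled z, no correction, all looks | 2.9-3.1% |
| Same z at interim 1, then adjusted estimate with uncorrected robust SE | 3.4-3.6% |
| SAP 5.4.4 corrected statistic at both interims, adjusted estimate with small-sample SE at the final look | 2.4-2.7% |
| SAP 5.4.4 corrected statistic at all looks | about 1.9% |

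Simulated power for the third procedure was 0.919-0.941, against 0.913-0.915 for the pooled unadjusted z.

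**The case against.** The case for leaving the plan alone is serious. An unadjusted comparison of two proportions is valid under randomisation, matches the stated hypothesis on the two proportions, and meets the planned power. No section contradicts another. The responder rule by itself contributes little: with score plus class, a mean of 76 and SD 13, and change unrelated to baseline, a second simulation found only 0.8-2.7% of variance explained. The upper end of the range needs an assumed relation between change and baseline that the documents do not supply. Adjustment also has a price, because a careless version breaks the 2.5% error rate. All of this stands, and it limits the point to one of efficiency.

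A reader might go further and infer that every baseline score has its own bar, that substantial precision is being lost, or that baseline imbalance biases the result. The documents support none of these. The bar takes four values. The loss cannot be sized from the documents. The unadjusted standard error already allows for chance imbalance, which moves the result by about 0.12-0.35 of a standard error for each standard error of imbalance.

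What the objection does not remove is that a predictor collected on everyone, built into the endpoint and already used for imputation has no place in any planned analysis of that endpoint's treatment difference among observed subjects.

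**Conclusion.** The point holds as a modest efficiency gain, and not as an error in the plan. Adjustment for baseline NOSE removes about 1-15% of the variance (median 3.5%), equivalent to about 1-19 of 124 subjects and 0.3-4 points of power (median about 1). These ranges rest on assumed baseline distributions, spreads of change and slopes, and on treating 30-50 as a class. They describe NOSE entered as categories; score plus class can recover somewhat less. The gain belongs at the final analysis. In single-look simulations at 60 subjects, power changed by -1.7 to +1.4 points, so there is no reason to adjust at the interims.

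**What to change.** 1. Complete the NOSE classes in the SAP, including where 30-50 and 0 belong. Until then the responder rule is ambiguous for baselines of 55 and 60.
2. Keep the continuity-corrected unadjusted statistic of SAP 5.4.4 at both interims.
3. At the final analysis, make the primary estimate the standardised risk difference from a logistic model with arm, baseline NOSE score and baseline class (55-75 v 80-100), with a robust standard error and a stated small-sample correction. This keeps the comparison of the two marginal proportions. Include the class term, since a linear score alone recovers little.
4. Before unblinding, confirm by simulation that overall one-sided error stays at 2.5%. The 2.4-2.7% above straddles that limit, so the exact form of the correction matters and should be chosen to pass the check.
5. Report the raw difference alongside. If the sponsor prefers the unadjusted test as primary, specify the same model as a sensitivity analysis.

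The cost is a paragraph in the SAP, a few lines of SAS, a short simulation and a slightly more complex primary analysis. Sample size, boundaries and data collection do not change. The choice must be fixed before unblinded results are seen, because an adjustment chosen afterwards would carry little weight.
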